13.2 Deprivation measures – Participant level

- Deprivation variables (all populations)

- IDACI 2015 national decile
- IDACI 2019 national decile
- IMD 2015 national decile
- IMD 2019 national decile

Derived using Lower super output area (LSOA)

Output areas (OA) are geographic areas created for Census data. There are, on average, around 1500 people living within each LSOA. Within our data a participant's LSOA will be determined by their postcode. The patient's LSOA will be used to determine a participant's level of deprivation (IMD & IDACI).

13.3 Derived Variables – Cluster level

- CYP population age <16 per GP cluster (routinely collected data)
- Paediatric OP referrals 2015-2016 per GP cluster (routinely collected data)

14. PARTICIPANT AND CLUSTER CHARACTERISTIC REPORTING

14.1 Baseline characteristics and balance between trial arms

The following restriction and stratification factors were used in the randomisation: IMD, IDACI, CYP population, OP referrals at baseline, Borough.

Demographic and clinical baseline characteristics and trial randomisation restriction and stratification factors at randomisation or recruitment will be summarised descriptively. We will report the number and percentage in each group for all categorical variables (**gender, age group, ethnicity, Health Check social questions, IMD decile, IDACI decile, Borough of GP registration**) and mean, SD, median, IQR, and range for all continuous variables (**age, CYP population <16 per GP cluster, Paediatric OP referrals 2015-2016 per cluster**). No significance testing will be carried out due to the randomised nature of the study.

15. EQUITY OF OUTCOMES ANALYSES

Some interventions, although they are beneficial overall, can widen inequality gaps. CYPHP aims to reduce inequality gaps.

Objective: To examine the impact of the CYPHP model of care on gradients (or variation) in health service use, physical and mental health, condition symptoms, health-related quality of life, parental well-being, and school/work absence.

To determine the impact of CYPHP on inequality gaps, we will examine differential intervention (moderator) effects, by adding an interaction term between measures of social disadvantage (listed below) and the study arm (intervention/control) variable, to the models estimating the impact of CYPHP on the study outcomes (listed below).

Measures of social disadvantage:

- IMD quintile (treated as ordered categorical variable)
- IDACI quintile (treated as ordered categorical variable)
- Ethnicity (Categories: White, Black, Asian, Mixed, Other)
- Health Check questionnaire responses regarding:
 - Housing concerns
 - Enough food for family

- Struggle to pay bills
- Parental mental health concerns

Outcomes: Health service use rates, PedsQL, CHU9D, ACT, POEM, Constipation, WEMWBS, SDQ, school/work absence

These will be explored with separate models, each model including one measure of disadvantage, as we expect these measures of disadvantage to be highly correlated. However, for ethnicity and parental mental health concerns, we plan to also adjust for socioeconomic status, to assess if there is an additional effect of these factors beyond their correlation with socioeconomic status, using IMD, IDACI, and/or a Health Check measure.

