10.9 Health Service Use Analysis Methods

The population analyses will assess the effects of the CYPHP model on health service use for CYP with any (or no) health condition.

Main analysis: cRCT Intervention vs. control analysis

- Populations: See section 8
- Time period: See section 7
- Comparator: Study arm (Intervention vs Control)
- Endpoints: Rates of health service use (listed and defined in sections 9-10)
- Summary statistics: estimate of intervention effect, estimates of covariate coefficients, 95% confidence intervals, p-values

Formal analysis: Multi-level Poisson regression model

- Individual level covariates: age, sex, IMD 2015, IDACI 2015, Borough
- Cluster level covariates: IMD 2015, IDACI 2015, baseline rate of health service use endpoint, number of CYP under 16 per cluster, Rate of paediatric OP referrals 2015-16, Borough
- Data structure:
 - Individual data: Pt Identifier, Cluster, Study arm (Intervention/Control), Number of HSU events during observation period, Observation time (days), Rate of HSU events during trial, Age at baseline, Sex, IMD 2015, IDACI 2015, Borough of GP registration, Number of HSU events during baseline period, Length of baseline period (days), Baseline rate of HSU events
 - Cluster data: IMD 2015, IDACI 2015, baseline rate of health service use endpoint, number of CYP under 16 per cluster, Rate of paediatric OP referrals 2015-16, Borough

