11.10 Intracluster correlation and regression models

Above we have described planned random-effects regression models, to account for clustering by randomised GP cluster. However, when we observe minimal correlation within clusters, these models are not appropriate, and we will report results from standard regression models, controlling for both the individual-level and cluster-level covariates described above.

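### The Poisson model for service use makes no provision for extra-Poisson variation between children, so the arm-by-disadvantage intervals in section 15 are too narrow if counts are overdispersed

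*SAP*

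**What the plan says.** SAP section 10.9 gives one model for all service-use rates: "Formal analysis: Multi-level Poisson regression model". Each child contributes one record, holding "Number of HSU events during observation period, Observation time (days") and covariates. The child-level adjustment is "Individual level covariates: age, sex, IMD 2015, IDACI 2015, Borough". The child's own baseline rate is in the data set but is listed as a covariate only at cluster level. Section 10.9 does not say what the levels are. It names no negative binomial model, dispersion parameter, child-level random effect or robust variance. It promises confidence intervals and p-values for the covariates as well as for the arm effect.

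The only random effect described anywhere is the GP cluster. Section 11.10 refers to "planned random-effects regression models, to account for clustering by randomised GP cluster" for the questionnaire outcomes, and section 12.2 uses the same clustering for the asthma quality indicators.

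Section 15 builds the equity analysis "by adding an interaction term between measures of social disadvantage (listed below) and the study arm (intervention/control) variable, to the models" already specified, with "each model including one measure of disadvantage". It lists seven measures: IMD quintile, IDACI quintile, ethnicity and four Health Check answers. The outcome list is "Outcomes: Health service use rates, PedsQL, CHU9D, ACT, POEM, Constipation, WEMWBS, SDQ, school/work absence". Only the first entry in that list uses the Poisson model.

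**The concern.** Children who use services often tend to go on doing so. Their counts then vary more than a Poisson model allows, and age, sex, deprivation and borough are unlikely to explain all of it.

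For the arm effect, a cluster random intercept largely deals with this, because the arms are compared between clusters. An interaction between arm and a child-level factor is different. It is estimated largely from contrasts between children in the same cluster, and a cluster intercept cancels out of those contrasts. Its standard error then rests on the Poisson variance alone.

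A second gap is related. The arm was allocated by cluster, so a comparison of deprivation gradients between arms needs to reflect how much gradients differ from cluster to cluster. No random slope is specified.

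Section 15 states that narrowing inequality is an aim of the programme and warns that interventions can widen gaps. Intervals that are too narrow could support a claim in either direction that the data do not justify.

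**Working it through.** **1. The plan's own figure.** The only stated figure for a service-use rate is the power for admissions in section 5.1: over 87% for a 20% reduction, 11 clusters per arm, 3,800 children per cluster and coefficient of variation 0.142. The baseline rate is not given. The standard cluster-trial formula for rates, with the usual one-cluster correction and two-sided 5%, is

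z_power = sqrt{(11 − 1)(λ0 − λ1)² / [(λ0 + λ1)/3800 + 0.142²(λ0² + λ1²)]} − 1.96.

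With λ0 = 0.053 and λ1 = 0.8 × 0.053 = 0.0424 per child-year, this is sqrt{10 × 0.0001124 / (0.0000251 + 0.0000929)} − 1.96 = 1.126, or 87.0%. So the stated power is consistent with a rate near 0.053 (0.036 without the correction). That back-solved rate is used below; it is not a figure in the SAP.

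**2. Effect of overdispersion on a within-cluster interaction.** If the variance is φ times the mean, the true standard error is sqrt(φ) times the reported one. A nominal 5% test on one degree of freedom rejects with probability 2Φ(−1.96/sqrt(φ)). The SAP states no significance level; two-sided 5% is assumed.

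| φ (assumed) | true SE / reported SE | 1 df | 4 df |
|---|---|---|---|
| 1.1 | 1.05 | 6.2% | 7.1% |
| 1.5 | 1.22 | 11.0% | 17.6% |
| 2 | 1.41 | 16.6% | 31.5% |
| 5 | 2.24 | 38.1% | 75.5% |

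The 4 df column applies if a five-category measure is tested without assuming a trend. Section 15 calls the quintiles ordered categorical and does not fix the test.

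**3. What φ might be.** With a gamma frailty of variance θ between children, φ = 1 + θ × rate × E[T²]/E[T]. Observation time T is taken as uniform from 30 days (the minimum in section 8.1) to 2.25 years (the 27 months in that section). Then E[T] = 1.17, E[T²] = 1.75, and the ratio is 1.50. The rates other than 0.053, and every θ, are assumptions. The simulation column has no true interaction and uses 23 clusters of 3,800, cluster SD 0.142, a linear quintile trend and 500 to 600 runs. Its Monte Carlo error is about 1 point near 5% and up to about 2 points at the higher rates.

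| Outcome | rate/year | θ | φ | formula | simulated |
|---|---|---|---|---|---|
| Admissions | 0.053 | 2 | 1.16 | 6.9% | 6.0% |
| Admissions | 0.053 | 4 | 1.32 | 8.8% | 8.8% |
| Admissions | 0.053 | 8 | 1.64 | 12.6% | 14.2% |
| Intermediate | 0.4 | 1 | 1.60 | 12.1% | 12.4% |
| Frequent contacts | 3 | 0.5 | 3.25 | 27.7% | 24.4% |
| Frequent contacts | 3 | 1 | 5.51 | 40.3% | 40.8% |

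With standard errors that allow for child-level variation, the simulated rate returns to between 4.5% and 6.2% in these scenarios. Section 7.1 ends the trial in June 2021 rather than June 2020. The longer follow-up would raise φ.

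**4. Gradients that differ between clusters.** If the log-rate slope per quintile has SD s across clusters, the effective φ rises by about s² × m × μ × V, where m is children per cluster, μ the mean count and V the variance of the quintile score (2 if the fifths are equal). Take s = 0.03, a purely assumed value, m = 3,800 and μ = 3 × 1.17 = 3.5. The addition is 0.0009 × 3800 × 3.5 × 2 = 24, so φ ≈ 25 even without child heterogeneity. The formula gives 69% and simulation 68%. Child-level robust errors leave it at 68%; comparing cluster-specific slopes by t-test gives 5.8%. With m = 87 (the consented target of 2,012 over 23 clusters), the addition is only 0.0009 × 87 × 3.5 × 2 = 0.55. At θ = 1 this moves the rate from 40% to 43%. Slope variation therefore matters for population-wide measures and little in small samples.

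**5. The main arm effect.** For admissions, the Poisson variance of a cluster's log rate is 1/(3800 × 0.062) = 0.0043, where 0.062 = 0.053 × 1.17. At φ = 1.32 it becomes 0.0056. Both are small beside the between-cluster variance 0.142² = 0.0202, and an estimated cluster variance takes up most of the difference.

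**The case against.** The strongest reply is that section 10.9 never says the random effect is at cluster level only. Multi-level is left undefined, and a child-level effect is not excluded. A reader might infer that the plan commits to treating a child's repeat events as independent. It does not say so; that follows only if the model has a cluster intercept alone. What stands is that no other structure is described anywhere, so an analyst following the text would most naturally fit that model.

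A reader might also infer that false findings of widening or narrowing gaps will be common. The document does not support this. It gives no event rate, dispersion or slope variance, and for admissions the inflation is modest over a plausible range. Section 15 says interactions will be explored and sets no significance level or decision rule, and equity is not among the purposes in section 2. The objection is right on all of this.

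It is also right that four of the seven measures are Health Check answers, which section 13.1 confines to tracer-condition populations. Calculations with about 3,800 children per cluster do not apply to them. Where section 8.3 applies, events are further limited to 12 months, which lowers the mean count and hence the dispersion.

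None of this removes the mechanism. Where counts are overdispersed and only the cluster is modelled, the interaction intervals are too narrow, and a cluster intercept does not repair them.

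**Conclusion.** The point holds as a gap in section 10.9 that section 15 inherits, and it should be fixed. If the model has a cluster intercept only, service-use interaction standard errors are too small by about sqrt(variance/mean).

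The size is unknown until dispersion is reported. Under the assumed values, the false-positive rate of a nominal 5% test is about 6–9% for admissions at frailty variance 2 to 4 and 14% at 8. It is about 24–41% for contacts averaging 3 a year.

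The individual-covariate p-values promised in section 10.9 share the fault. The questionnaire outcomes do not use this model, and the main arm comparison is affected only slightly. The documents give no ground for saying that the primary population result is undermined.

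**What to change.** In section 10.9, state the random effects and replace plain Poisson with a model that allows overdispersion between children: negative binomial, or Poisson with a child-level random effect, with the GP cluster effect kept. Say that the same model carries into the section 15 interactions for service-use rates, and report the estimated dispersion.

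For the population-wide measures (IMD, IDACI and ethnicity), also let the disadvantage gradient vary by GP cluster. Alternatively, estimate it within each cluster and compare 11 with 12 clusters by t-test as a sensitivity analysis. For the Health Check measures the overdispersion term is the part that matters; cluster-specific gradients would be noisy in samples of that size.

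The cost is a few sentences in the SAP, somewhat more complex fitting and wider interaction intervals. No new data are needed. If the counts prove close to Poisson and the gradients similar across clusters, the results will change little.

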11.9 Analysis Methods

Analysis (for 6-month and 12-month follow-up): Random-effects regression models. Covariates at individual level: participant age group, sex, IMD 2015 quintile, IDACI 2015 quintile, Borough, and the baseline questionnaire outcome score. Covariates at cluster level: mean IMD 2015, mean IDACI 2015, number of children under 16 years, rate of paediatric OP referrals 2015-16, and the mean baseline questionnaire outcome score.

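### The equity step meant to separate moderation by ethnicity and parental mental health from socioeconomic status (SES) specifies no arm-by-SES term, and a covariate adjustment cannot do that job

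*SAP*

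**What the plan says.** Section 15 looks for differential intervention effects "by adding an interaction term between measures of social disadvantage (listed below) and the study arm (intervention/control) variable" in the models that estimate the effect of CYPHP. The measures of disadvantage are taken singly: "each model including one measure of disadvantage, as we expect these measures of disadvantage to be highly correlated". Two measures get a further step: "for ethnicity and parental mental health concerns, we plan to also adjust for socioeconomic status, to assess if there is an additional effect" over and above their correlation with SES. The SES measure for that step is left open: "using IMD, IDACI, and/or a Health Check measure". The section does not say whether SES enters this step as a main effect only or also with its own arm interaction.

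The models to which these terms are added already hold deprivation. For health service use, Section 10.9 has "Individual level covariates: age, sex, IMD 2015, IDACI 2015, Borough". For the questionnaire outcomes, Section 11.9 has "participant age group, sex, IMD 2015 quintile, IDACI 2015 quintile, Borough, and the baseline questionnaire outcome score".

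**The concern.** The question in Section 15 is about moderation: does the effect of CYPHP vary by ethnicity, or by parental mental health concern, for reasons other than deprivation? The rival explanation is moderation by deprivation, so the model has to contain that rival, which is arm × SES. A covariate allows the outcome level to differ by SES but not the treatment effect.

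The wording points to a covariate. Section 15 names an interaction term when it means one, and Section 10.1 uses the same verb, adjust, for ordinary patient-level covariates. At stake is the interpretation of an equity finding. A programme that narrows gaps by deprivation could be credited with an effect specific to ethnicity or parental mental health, and the step meant to guard against this would not do so.

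**Working it through.** The SAP states no figure on this point, so there is none to reproduce. The check has three parts.

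**1. Redundancy.** Section 15 adds its terms to the effect models, and those already contain individual-level IMD and IDACI. For questionnaire outcomes both are in quintiles, so adding either again as a main effect leaves the model unchanged. For health service use the same holds, apart from any change in how the index is coded. Section 13.1 gives Health Check social responses for the tracer condition populations only, so in the whole-population models IMD and IDACI are the only listed SES measures available. A Health Check item would be a new covariate where it exists, but part 2 applies to it too.

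**2. Algebra.** Let A be arm, E a two-level group (ethnicity or parental concern) and S the deprivation quintile. Suppose there is no true moderation by E:

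Y = a + bA + cS + γ·A·S + error

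With A × E fitted and A × S omitted, randomisation makes A independent of (E, S) in expectation. The fitted A × E coefficient is then about

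γ × (mean S in E = 1 − mean S in E = 0).

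The main effect c does not appear. With A centred, A × E is uncorrelated with S, so adding S as a main effect leaves the A × E coefficient where it was.

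**3. Simulation.** Inputs from SAP Section 5.1: SD 16.5, arm effect 4.5 points, 2,012 recruited with 30% loss, so 2,012 × 0.7 ≈ 1,408. Assumed, because the documents give no values: two groups of equal size; a latent deprivation gap of 0, 0.5 or 1.0 SD; γ of 0, 1 or 2 points per quintile; a main effect of −2 points per quintile. Ordinary least squares without clustering, 2,000 runs, no true moderation by group. Model A has arm × group only; B adds quintile main effects; C adds arm × quintile as well. Entries are the mean spurious arm × group coefficient in points and the rejection rate at nominal 5%.

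| Gap (SD) | γ | A | B | C |
|---|---|---|---|---|
| 0 | 0 | −0.02; 4.4% | −0.02; 4.6% | −0.01; 4.5% |
| 0 | 2 | 0.00; 5.2% | 0.00; 5.2% | 0.01; 5.0% |
| 1.0 | 0 | 0.04; 5.0% | 0.03; 4.6% | 0.01; 5.3% |
| 0.5 | 1 | 0.66; 7.2% | 0.66; 7.2% | 0.02; 5.8% |
| 0.5 | 2 | 1.30; 10.6% | 1.30; 10.7% | −0.03; 4.4% |
| 1.0 | 1 | 1.19; 10.2% | 1.18; 10.4% | −0.04; 4.6% |
| 1.0 | 2 | 2.52; 29.5% | 2.52; 29.6% | 0.00; 5.4% |

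A and B agree within 0.01 points throughout, so the SES main effect removes none of the bias. C removes it. Section 11.1 analyses PedsQL as z-scores; on that scale the bias is 0.66/16.5 = 0.04 to 2.52/16.5 = 0.15 SD. Monte Carlo error on a 5% rate is √(0.05 × 0.95/2,000) ≈ 0.5 percentage points.

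Bias does not shrink with sample size, but false positives grow. At an illustrative 20,000 (300 runs), model B rejected in 30% to 100% of runs in the four scenarios with both a gap and moderation.

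**The case against.** The strongest reply is that Section 15 may already intend the joint model. The base models carry both IMD and IDACI, so the statement "These will be explored with separate models, each model including one measure of disadvantage" cannot describe main effects and makes sense only as one moderator per model. The next sentence opens as an exception to that rule, so SES could be joining as a second moderator. The redundancy shown above is itself a reason to doubt the covariate reading. This stands to the extent that the form is unstated. A reader might infer that the SAP rules out an arm × SES term; it does not.

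A second reply is that bias needs both real moderation by deprivation and a deprivation gap between groups. That is right: with either absent, the table shows no bias. The SAP expects its disadvantage measures to be highly correlated but gives no value, and gives none for moderation. The larger scenarios are demanding: 2 points per quintile is 2 × 4 = 8 points from first to fifth quintile, against a planned difference of 4.5. The simulation also uses two groups where Section 15 has five ethnic categories, and ignores clustering. These points limit the figures, not the algebra.

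Third, if benefit differs by deprivation and ethnic groups differ in deprivation, the ethnic gap really does change, and arm × ethnicity alone describes that correctly. This also stands. The single-measure models answer the section's main objective.

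**Conclusion.** The point holds for the additional-effect step only. Section 15 asks for moderation beyond SES and specifies no term that could deliver it. On the natural reading the step is redundant with IMD or IDACI, and ineffective with any SES measure entered as a main effect. On the generous reading the model is right but unwritten. Both call for the same edit.

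A reader might go further and conclude that the trial will report false moderation by ethnicity or parental mental health. The documents do not support that: the form of adjustment is an inference, and the consequence depends on two quantities they do not give. Under the assumed range the false-positive rate at 1,408 completers runs from about 5% with no gap or no moderation to about 7% to 30% with both. No size is offered for count or binary outcomes, where the same reasoning applies on the log or logit scale.

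This is a secondary, exploratory analysis and no primary estimate is touched. Because the SES measure is also open, the analyst could choose it after seeing results across many outcomes.

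**What to change.** Replace the sentence in Section 15 with a stated model. For ethnicity and for parental mental health concerns, a second model will contain arm × ethnicity (or arm × parental concern) and arm × SES together, with all main effects; the additional moderating effect is the former interaction in that joint model.

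Name one SES measure for this step in place of the open list. IMD quintile is one option, with its arm interaction either as a linear trend (one term) or in categories (up to four terms); say which. It is available in every population but is area-level (Section 13.2). A household Health Check item could serve instead in the tracer condition populations, provided it is fixed in advance. Keep the single-measure models as the description of changing gaps.

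The cost is one sentence and slightly wider intervals for the interaction of interest. The standard error grows by about 1/√(1 − R²), where R² is the share of the group indicator explained by SES. At the assumed latent gaps, R² is at most 0.0625/1.0625 = 0.06 and 0.25/1.25 = 0.20, so intervals widen by at most about 3% and 12%.
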